**Trial Design**

This is a pivotal study to assess long-term (~1 year) efficacy of setmelanotide in LEPR deficiency obesity. The study will begin with an initial period of dose titration lasting between 2 and 12 weeks where the individual patient's therapeutic dose will be established by upwards dose titration in 2-week intervals. Thereafter, patients will continue active treatment at their individually titrated optimal therapeutic dose for an additional 10 weeks, for a total combined dosing duration of 12 weeks at the individual patient's therapeutic dose [i.e., the last 2 weeks during dose titration plus 10 weeks of open label treatment]. For patients who demonstrate at least 5 kg weight loss (or at least 5% weight loss if baseline body weight < 100 kg) at the end of the Open Label Treatment Period, they will continue onto the double-blind, variably-timed, placebo-controlled, withdrawal period lasting 8 weeks inclusive of a 4-week period of placebo treatment. The onset of the placebo period will be variable for each patient to mask the actual

timing of the withdrawal period. Following the 8-week withdrawal period, patients will continue dosing at their therapeutic dose for ~32 weeks, resulting in a total of ~52 weeks dosing at their therapeutic dose.
 
Where feasible, and for patients who agree to participate, there
 

Study Population
 
Male and female patients, 6 years of age and above, with a confirmed diagnosis of LEPR Deficiency Obesity due to bi-allelic, loss-of-function LEPR gene mutations.

Number of Patients & Study Centers
 
It is currently anticipated that a total of ~10 patients will be enrolled in this study. The total number of patients required for registration is yet to be confirmed with applicable regulatory authorities, given that true prevalence of this ultra-rare disease is uncertain. Therefore, the total number of patients may be increased or decreased to satisfy regulatory requirements for registration, depending upon the total number of affected patients identified.
 
It is anticipated that up to 10 centers located worldwide will participate in this study. If added patients are to be enrolled, additional sites may be added, as necessary.

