3. INVESTIGATIONAL PLAN

3.1. Overall Design and Plan of the Study

This is a pivotal Phase 3 study to assess long-term (1 year) efficacy of setmelanotide in LEPR deficiency obesity.

After providing informed consent, patients will enter the Screening Period. During the Screening Period, patients will be assessed for eligibility and instructed to complete a hunger questionnaire daily for a minimum of one week and ideally two weeks to establish a baseline and to enhance the understanding of hunger symptoms associated with LEPR deficiency obesity prior to treatment with setmelanotide. As LEPR deficiency is ultra-rare, obtaining daily hunger scores as well as a very detailed medical history (medical record review) during Screening will allow for the collection of important patient specific data (see Appendix 11.3; e.g., growth and weight curves, other associated [REDACTED] abnormalities, pediatric developmental milestones or disturbances, and possible orthopedic or respiratory complications due to weight gain) that will allow for a better understanding of this rare monogenic form of obesity.

After the Screening Period, there are four treatment phases to the study:

Open Label Dose Titration Phase (2 – 12 weeks)

In this phase of the study, a patient's individual therapeutic dose will be established. The starting dose is 1.0 mg for adult patients and 0.5 mg for adolescent and 0.25 mg for pediatric patients.

Patients will return to the clinic every two weeks to assess their weight loss and hunger scores and dosing will increase every two weeks in 0.5 mg increments until a patient's individual therapeutic dose is established per the guidelines in Appendix 11.8.

As this is a global study, the maximum allowable dose differs across countries based on feedback from competent authorities. The US, UK and the Netherlands have approved a maximum dose of 3.0 mg, while Germany and France have approved a maximum dose of 2.5 mg. Therefore, the duration of the dose titration stage will range from 2 to 12 weeks, depending on the number of escalations required to define the therapeutic dose and the approved maximum dose in the country of the participating site.

Open Label Phase (10 weeks)

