After establishing a patient's individual therapeutic dose, the patient will continue dosing for an additional 10 weeks, resulting in 12 total weeks of treatment at their therapeutic dose (including the last 2 weeks at the therapeutic dose in the dose titration phase). To continue treatment after 12 weeks of treatment at their therapeutic dose, patients must achieve a weight loss of 5 kg or greater from baseline if their baseline weight was greater than 100 kg or a weight loss of > 5% from baseline if their baseline weight was < 100 kg. Patients who do not achieve these weight loss criteria will be discontinued from treatment, but should continue with other study procedures through study end.

[figure not shown]
Placebo-Controlled, Double-Blinded Withdrawal Phase (8 weeks)

Patients that achieve a 5 kg or 5% weight loss after 12 weeks of treatment at their therapeutic dose will receive either placebo or active for four weeks and then cross-over to the opposite treatment for four weeks. The treatment assignment during the first four-week period will be double-blinded so that the sites and patients do not know if their first four-week block of treatment is placebo or active.

Open Label Treatment Phase (32 weeks)

After completing the placebo-controlled, double-blinded withdrawal phase, patients will continue dosing at their individual therapeutic dose for an additional 32 weeks. At the end of the 32 weeks, patients can enroll in a separate long-term extension study to continue receiving setmelanotide (Study RM-493-022) or they can complete treatment with a final visit approximately 30 days after their last dose.

Figure 7: Study Schema

It is anticipated that at least 10 patients will be enrolled in this study. However, due to the ultra-rare prevalence of this population, if more patients are identified during the conduct of the study, they may also be enrolled.

In addition, for patients at sites where feasible, and who agree to participate, [REDACTED]

[REDACTED]

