[REDACTED] Menarche and menstrual history will be obtained in all females. Adrenarche staging will be performed. Testicular volumes will be documented by the Prader methodology for males, and breast development will be documented for females. Height will be measured during the Screening Period only for those patients \geq 18 years of age. Height will be measured per the [SOA](#) for those patients $<$ 18 years of age. Height (cm) will be measured, without shoes, socks or hats according to the SOA using a wall-mounted stadiometer. All measurements will be done in triplicate at each timepoint and recorded to the nearest 10th of a decimal place. The stadiometer should be calibrated at the time of use or within the previous four hours.

2 A comprehensive skin evaluation will be performed by a dermatologist. Any concerning lesions identified during the screening period will be biopsied and results known to be benign prior to first dose of setmelanotide. If the pre-treatment biopsy results are of concern, the patient will be excluded from the study.

3 Optional sub-studies for Investigative Sites that can perform these assessments and have patients willing and able to participate. In the event a site can perform multiple sub-studies, care needs to be taken in order to not overburden with multiple additional assessments/visits.

4 Urine pregnancy test may be performed to expedite availability of results prior to dosing on Dose Titration Day 1. All other pregnancy tests will be serum; dosing may continue with results pending.

5 Prior to study drug administration.

6 The Dose Titration phase will be a variable schedule lasting a minimum of 2 weeks and a maximum of 10 weeks, in which patients will return to the clinic approximately every 2 weeks to establish the individual patient's therapeutic dose per Appendix 11.8. Given the variable number of dose titration steps in the Dose Titration Phase, each Dose Titration Visit Number (V) will remain V2 with an alphabetized suffix added to each titration visit (i.e.; first dose titration at start of Week 1 = V2a, second dose titration at start of Week 3 = V2b, etc.). This will allow for the Visits to be appropriately tracked. Additionally, each dose titration visit will have the same pre- and post-dose assessments as outlined in the [SOA](#) (except for Anti-RM-493 antibodies and [REDACTED])

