18 Safety laboratories will include: CBC with platelet count and standard indices, chemistry panel (includes sodium, potassium, chloride, CO₂, albumin, total protein, glucose, BUN, creatinine, uric acid, AST, ALT, GGT, CPK, alkaline phosphatase, total bilirubin, direct bilirubin, LDH, calcium, phosphorus), urinalysis with microscopic analysis if positive findings on dipsticks warrant further examination. Safety laboratories shall also include a coagulation profile (prothrombin time [PT] or international normalized ratio [INR], and partial thromboplastin time [PTT], also referred to as activated partial thromboplastin time [aPTT]. Fasting samples (8 hours minimum) are required at all timepoints where feasible. [REDACTED] and HbA1c will also be included.

19

20 Daily hunger questionnaire scores will be assessed by asking the patient to score their hunger
[REDACTED] Daily hunger questionnaire scores will be recorded daily, prior to the patient's morning meal.

21 [REDACTED]

22 [REDACTED]

23 Body composition may be performed using an appropriate method available at sites (e.g. BIA, DXA, etc.). Refer to Section 6.3.3 regarding appropriate methodology for assessing this patient population.

24 Once all the pre-dose assessments have been performed, the decision to dose titrate per Appendix 11.8 will be made. If the patient's therapeutic dose has been established, the patient will transition into the 10-week Open Label Active Treatment Phase, receive their therapeutic dose, and complete the V3 post-dose assessments as defined in the SOA. If the patient's therapeutic dose has not been established per Appendix 11.8, the patient will be administered study drug, complete the dose titration post-dose assessments as defined in the V2 SOA, and return to the clinic in ~2 weeks for the next sequential Visit 2 (i.e.; V2b, V2c, etc.).

25 Adverse events will be recorded from the time a patient provides informed consent. AEs reported after dosing on Day 1 will be considered treatment-emergent AEs.

26 Any patients with positive anti-drug antibodies will be followed ~every 3 months until titers resolve or return to baseline.

27 Telephone contact by site monthly, or more frequently, if needed.

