7. ADVERSE EVENTS

Monitoring of adverse events will be conducted throughout the study. Adverse events will be recorded in the CRFs from Screening through the Final Study Visit. Adverse events that occur after the start of study drug administration will be considered treatment emergent adverse events (TEAEs). SAEs will be recorded through the Final Study Visit. All adverse events should be monitored until they are resolved or are clearly determined to be due to a patient's stable or chronic condition or intercurrent illness(es).

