8.2. Statistical Methods

Statistical methods, populations and approaches to address multiplicity of secondary endpoints and missing data will be outlined in the SAP.

The primary analysis will be conducted based on a Full Analysis Set (FAS), which is defined as all subjects who received at least 1 dose of study medication and have a baseline measurement (regardless of whether at least one post-baseline efficacy assessment is observed). All available measurements (including data from patients who discontinue active treatment) will be included in the analysis. The comparison of post-treatment values versus baseline and of proportions to null hypothesis values will be carried out via 1-sided statistical test at an alpha=0.05. No adjustment for multiplicity is needed for the single primary endpoint (i.e. percent of patients who achieve at least 10% weight loss after 1 year of treatment versus the null hypothesis value of 0.05).

For the primary endpoint, and all other endpoints, the last value obtained prior to the first dose of active treatment will be considered the baseline value for statistical analyses.

As this patient population is extremely rare, all data collected, even if outside of visit windows, will be included in all analyses of endpoints.

AEs will be coded by using the most current version of Medical Dictionary for Regulatory Activities (MedDRA) and summarized by system organ class, preferred term, and treatment group for the number and percent of AEs reported, the number of patients reporting each AE, and the number of patients with any AE.

A by-patient AE data listing including onset and resolution dates, verbatim term, preferred term, treatment, severity, relationship to treatment, action taken, and outcome will be provided.

Safety data including laboratory evaluations and vital signs assessments will be summarized by time of collection and by treatment group. In addition, change from baseline to any post-dose values will be summarized for vital signs and clinical laboratory results. Frequency of patients with abnormal safety laboratory results will be tabulated by treatment.

Plasma concentrations will be summarized. Plasma concentrations may be compared to PD endpoints.

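### The by-treatment adverse event table in Section 8.2 has no time-at-risk denominator, although completers spend at least 12 times as long on setmelanotide as on placebo

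*Protocol*

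**What the plan says.** Protocol Section 8.2 states that adverse events (AEs) will be "summarized by system organ class, preferred term, and treatment group for the number and percent of AEs reported", together with the number of patients reporting each event and the number with any event. Laboratory data follow the same pattern: "Frequency of patients with abnormal safety laboratory results will be tabulated by treatment". Neither sentence mentions exposure time or matched periods, and *treatment group* is not defined.

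The design has no parallel groups. Section 5.3 puts every patient on active drug except during the withdrawal phase. The synopsis describes that phase as a "withdrawal period lasting 8 weeks inclusive of a 4-week period of placebo treatment", and Section 3.1 makes it a within-patient crossover of four weeks on each treatment. Only patients who meet the weight-loss criterion enter it.

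Treatment-emergent events are defined twice. Section 7 goes by when the event occurs, after the first dose. Footnote 25 of Table 6-1 goes by when it is reported: "AEs reported after dosing on Day 1 will be considered treatment-emergent AEs".

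**The concern.** A crude table by treatment is readable when groups are followed for similar times. Here the two columns would be two states of the same patients, one lasting about a year and the other four weeks. Time at risk alone would then fill the drug column, whether or not the drug causes the events.

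Safety and tolerability is a named secondary objective of a pivotal study. The number of patients is too small for a reader to correct such a table by eye.

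**Working it through.** **Phase lengths (Sections 3.1 and 5.5).** Screening 2-4 weeks, titration T = 2-12, open label 10, blinded phase 8 (4 placebo + 4 active), open label 32.

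**Check against the plan's own total.** Section 5.5 gives about 54 to 66 weeks of participation.
- Minimum: 2 + 2 + 10 + 8 + 32 = 54.
- Maximum: 4 + 12 + 10 + 8 + 32 = 66.

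Both are reproduced.

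**Time on each treatment, completing responder.** Drug = T + 10 + 4 + 32 = T + 46 weeks; placebo = 4 weeks.

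| Titration T | Weeks on drug | Drug : placebo | Share of events under drug at equal rates |
|---|---|---|---|
| 2 | 48 | 12.0 | 48/52 = 92.3% |
| 10 | 56 | 14.0 | 56/60 = 93.3% |
| 12 | 58 | 14.5 | 58/62 = 93.5% |

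The T = 10 row is needed because footnote 6 of Table 6-1 describes titration as "lasting a minimum of 2 weeks and a maximum of 10 weeks", and Section 5.2 agrees, while Sections 3.1 and 5.5 allow 12 weeks. Those passages need to be reconciled.

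**Non-responders.** Section 3.1 says that after titration "the patient will continue dosing for an additional 10 weeks, resulting in 12 total weeks of treatment at their therapeutic dose", so a patient stopped at that point has T + 10 = 12 to 22 weeks on drug and none on placebo. If 2 of 10 patients are non-responders and the rest complete, the ratio of total exposure is:
- T = 2: (8 × 48 + 2 × 12) / (8 × 4) = 408/32 = 12.75.
- T = 12: (8 × 58 + 2 × 22) / (8 × 4) = 508/32 = 15.9.

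With 5 of 10 it is 300/20 = 15 to 400/20 = 20. Non-responders widen the imbalance.

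**Percent of patients with an event, equal constant rate.** If a proportion q has the event in 4 weeks, the proportion expected in w weeks is 1 − (1 − q)^(w/4).
- q = 0.10: 1 − 0.9^12 = 72% at 48 weeks; 1 − 0.9^14.5 = 78% at 58 weeks.
- q = 0.05: 46% and 53%.

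**Expected counts, 10 completers, assumed equal rates.** Count = 10 × rate × weeks/52.

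| Events per patient-year (assumed) | Events on drug | Events on placebo | Patients with any, drug | Patients with any, placebo |
|---|---|---|---|---|
| 0.25 | 2.3-2.8 | 0.2 | 21-24% | 1.9% |
| 1 | 9.2-11.2 | 0.8 | 60-67% | 7.4% |
| 5 | 46-56 | 3.8 | 99-100% | 32% |
| 20 | 185-223 | 15 | 100% | 79% |

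The ratio of counts is always 12 to 14.5. The gap in percent of patients narrows for very frequent events, as both columns approach 100%.

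**With a time denominator.** Under equal rates, events per patient-week have an expected ratio of 1.0. So do counts from the 4-week placebo and 4-week active blocks of the blinded phase.

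**The case against.** The strongest reply is that no drug-placebo comparison of AEs is planned. Section 8.2 says that events are summarised. Its tests concern change from baseline and proportions against null values, and the synopsis speaks of one-sample summaries and per-patient listings. The placebo block exists to show reversal of weight and hunger. Section 8 leaves further analyses and conventions to the SAP, which is not at hand and may well add exposure-adjusted rates. All of this stands, and it limits the severity. It does not remove the point, because the crude by-treatment table is stated in the protocol rather than deferred, and setmelanotide versus placebo is the only treatment contrast in the design.

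Several stronger readings are tempting but unsupported:
- *Every patient has 48-58 weeks on drug and 4 on placebo.* This is true only of responders who complete. Non-responders have no placebo time, and Section 6.1 allows an early return to open-label drug. A responder who leaves at the end of the blinded phase has only T + 14 = 16 to 26 weeks on drug, a ratio of 4 to 6.5.
- *The matched four-week comparison is lost.* It is not planned, but it can be recovered: the by-patient listing in Section 8.2 carries onset date and treatment. Nor is it clean. The placebo block follows at least 12 weeks on drug, and Section 4.5 allows about 60-90 days for skin events to resolve, so carry-over is plausible.
- *Placebo-block events are mixed into the drug's profile.* A table split by treatment would separate them. Only events after stopping treatment lack a clear place.
- *The treatment-emergent window is open-ended, with some 40 weeks off drug.* Recording stops at the Final Study Visit. The 40 weeks (52 − 12) require non-responders to stay in follow-up. The synopsis and Sections 3.1 and 4.5 say they should. Section 6.1 says they are withdrawn from the study with an Early Termination Visit, although it then encourages withdrawing patients to complete the remaining visits.

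The difference between occurring and reported events is a minor wording mismatch. It affects only an event that starts before the first dose and is reported afterwards.

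**Conclusion.** The point holds in a limited form. As stated, the by-treatment AE table cannot be read as a comparison. Among completing responders the columns differ 12- to 14.5-fold in time at risk (12- to 14-fold under the 10-week titration limit), and adding non-responders raises the ratio. With equal event rates, 92-94% of completers' events would appear under drug.

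This rests on three assumptions: that *treatment group* means setmelanotide versus placebo, that responders complete, and, for the percentages of patients, that the event rate is constant. With 10 patients those percentages illustrate the distortion and do not predict results. It does not follow that the plan makes a biased drug-placebo claim, because it makes no such claim. The change is worth making, but the trial does not depend on it.

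**What to change.** In Section 8.2:
1. Replace *treatment group* with treatment received at event onset: setmelanotide, placebo block, or off drug after stopping.
2. Report events and patients for each state with the exposure time and per patient-time, and keep one crude column for all patients. Attribute laboratory abnormalities in the same way.
3. Show any setmelanotide-placebo contrast in AEs only within the 8-week blinded phase (4 weeks of each), descriptively, with a stated caution about small numbers and carry-over.

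Elsewhere:
4. Define treatment-emergent by onset date in both Section 7 and footnote 25 of Table 6-1.
5. Reconcile the synopsis and Sections 3.1 and 4.5 with Section 6.1 on whether non-responders stay in follow-up, and reconcile the two titration maxima, since both determine the exposure denominators.

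The cost is protocol or SAP wording and one extra table. The listing already calls for onset date and treatment, and the dosing diary is already kept, so no new data are needed. The downside is wide uncertainty in the four-versus-four-week view, which is why the all-patient column should stay.

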8.3. Timing of Analyses

It is planned that an analysis may be completed once all planned patients have completed ~1 year of treatment, data has been cleaned and finalized, and the database is locked for assessments (including the double-blind placebo-controlled withdrawal phase, the only part of the study which is not open label).

8.4. Long-Term Extensions and Pooling of Patients from other Studies

It is expected that LEPR deficiency patients who continue to tolerate setmelanotide after 1 year of treatment, and who show clinically important weight loss, will be continued in long-term extensions (to be fully outlined in a future extension protocol, as noted in Section 5.5), on a year by year basis. Additional analyses will summarize the long-term experience as appropriate.

It is also expected that some patients may not enter this study (for logistical reasons) but will be participating in an essentially identical protocol (Study RM-493-011) with a long-term extension phase. After assessing that study conduct and upon determining essentially identical treatment procedures to this study, these patients will also be carefully identified in the Clinical Study Report. Their data will also be summarized and pooled with data from patients who entered this pivotal study in a supplemental analysis.

8.5. Statistical Analysis Plan

The full Statistical Analysis Plan for this study will provide more detailed statistical procedures prior to any planned analysis.

9. ADMINISTRATIVE REQUIREMENTS

9.1. Good Clinical Practice

The study will be conducted in accordance with the International Council on Harmonization (ICH) for Good Clinical Practice (GCP) and the appropriate regulatory requirement(s). The Investigator will be thoroughly familiar with the appropriate use of the study drug as described in the protocol and IB. Essential clinical documents will be maintained to demonstrate the validity of the study and the integrity of the data collected. Master files should be established at the beginning of the study, maintained for the duration of the study and retained according to the appropriate regulations.

